5.11.3.2.3 Descriptive analysis

In addition, a descriptive summary of observed MITOS stage values at baseline, Month 3 and Month 6 as well as their change from baseline to month 3 and to month 6 will also be provided.

5.11.4 Change in King's College stage

5.11.4.1 Expressions

This parameter will be expressed in terms of:

- Value at baseline and at each planned visit (V3, and V4).
- Change from baseline to each post baseline visit.
- Change from V3 to V4.

STATISTICAL ANALYSIS PLAN		
InFlectis BioScience	Sponsor:	InFlectis BioScience
	Protocol Number:	P288ALS
VERSION 1.0 NOV 12, 2024		

5.11.4.2 Change in King's College stage at Month 6 (V4)

5.11.4.2.1 Primary analysis

The primary analysis of the Change in KCL stage from baseline to Month 6 will be conducted on the FAS as described in Table 3Erreurs ! Source du renvoi introuvable.. The Change in KCL stage will be analyzed as a binary endpoint defined as the progression (versus non-progression) of the KCL stage to a higher stage at 6 months compared to baseline. Hence, subjects who did not progress to a higher stage at 6 months compared to baseline stage are “non-progressors”. “Non-progressors” will be modelled in the analysis.

Missing data at month 6 whichever reason (death or drop-out prior to month 6) will be imputed as progressors (i.e. with a higher stage at month 6 compared to baseline stage).

The difference in rates of “non-progressors” at month 6 between IFB-088 vs placebo along with 95% CIs and p-value will be estimated according to the binomial exact method.

The ratio of rates of “non-progressors” at month 6 between IFB-088 vs placebo along with 95% CIs and p-value will be estimated according to the binomial exact method.

5.11.4.2.2 Supportive analysis

The same analysis will be repeated on the PPS.

5.11.4.2.3 Descriptive analysis

In addition, a descriptive summary of observed King's College stage values at baseline, Month 3 and Month 6 as well as their change from baseline to month 3 and to month 6 will also be provided.

5.11.5 Analysis of biomarkers

Analyses will be done on the FAS.

5.11.5.1 Parameters

- TDP-43 plasmatic concentration
- Neurofilament (NfL) light chain
- NfL heavy chain plasmatic concentration
- Growth differentiation factor 15
- Interleukin IL-6
- Tumour necrosis factor- α
- Interferon γ
- IL-1 β

STATISTICAL ANALYSIS PLAN		
InFlectis BioScience	Sponsor:	InFlectis BioScience
	Protocol Number:	P288ALS
VERSION 1.0 NOV 12, 2024		

- IL-8
- IL-10
- Monocyte chemoattractant protein-1
- Nerve growth factor
- Brain-derived neurotrophic factor
- Vascular endothelial growth factor
- Transforming growth factor beta 1
- Transforming growth factor beta 2
- Transforming growth factor beta 3
- 8-hydroxy 2 deoxyguanosine
- Fibroblast Growth Factor 21
- NGFR/p75ECD
- Neopterin
- Creatinine

5.11.5.2 Expressions

These parameters will be expressed in terms of:

- Log10 value at baseline, V3 at V4.
- Change from baseline to V3 of log10 value.
- Change from baseline to V4 of log10 value.

Note: TDP-43 plasmatic concentration, Neurofilament (NfL) light chain and NfL heavy chain plasmatic concentration parameters are not collected at V3.

Values “above limit of quantification” (ALQ) will be imputed by ULOQ and values “below limit quantification” (BLQ) will be imputed by LLOQ.

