5.11.5.2.1 Analysis of NFL

NFL missing values will not be imputed.

As NFL distribution might be rather skewed with extreme values, NFL assessed at baseline and at month 6 will be log10 transformed. A descriptive analysis will be performed on the log10-scale and then back-transformed: geometrical means and their 95% Cis will be provided.

NFL (log10 transformed) at month 6 will be analyzed in an ANCOVA model adjusting for treatment and baseline NFL (log10 transformed). Adjusted means and the difference in adjusted means will be estimated in this model and then back transformed into the original scale. Adjusted mean NFL at month 6 in each treatment is interpreted as a geometric mean (adjusted for baseline

STATISTICAL ANALYSIS PLAN		
InFlectis BioScience	Sponsor:	InFlectis BioScience
	Protocol Number:	P288ALS
VERSION 1.0 NOV 12, 2024		

NFL). The back transformed adjusted treatment difference is interpreted as the ratio of adjusted geometric means between treatments.

A descriptive analysis will only be performed on the log10-scale and then back-transformed: geometrical means and their 95% CIs will be also provided at 3 months.

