5.11.5.2.2 Analysis of TDP-43

TDP-43 will be analyzed with the same approach as for NFL on the FAS.

5.11.5.2.3 Other biomarkers.

A descriptive analysis will only be performed on the log10-scale and then back-transformed: geometrical means and their 95% Cis will be provided on the FAS.

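### Analysing NfL light chain and TDP-43 values below quantification as if they equalled the LLOQ pulls a true treatment ratio towards 1 and makes the 95% CI under-cover, if such values are common

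*SAP*

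**What the plan says.** SAP 5.11.5.2 sets one rule for all biomarkers. Values above the quantification range are replaced by its upper limit ("ALQ) will be imputed by ULOQ and values") and values below it by its lower limit ("BLQ) will be imputed by LLOQ").

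SAP 5.11.5.2.1 then specifies the model for NfL, which the SAP abbreviation list defines as the light chain: "NFL (log10 transformed) at month 6 will be analyzed in an ANCOVA model adjusting for treatment and baseline NFL (log10 transformed"). On the effect measure it says: "The back transformed adjusted treatment difference is interpreted as the ratio of adjusted geometric means between treatments". SAP 5.11.5.2.2 extends this to TDP-43: "TDP-43 will be analyzed with the same approach as for NFL on the FAS". The remaining biomarkers are described only. NfL heavy chain is not named in any model, so it appears to belong with them.

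SAP 5.11.5 contains no censored-data model, no sensitivity analysis for the substitution, no upper limit on the share substituted and no count of substituted values. The sentence "NFL missing values will not be imputed" concerns absent values, not values known to lie beyond a limit.

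**The concern.** A result below the LLOQ says only that the concentration lies somewhere under that limit. Placing all such results on one number discards whatever part of a treatment difference lies below it, and it reduces the residual variance, so the interval narrows as information is lost. If the drug lowers a marker, the active arm has more values below the limit, so the loss is greater in that arm.

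Effect on biomarkers is a stated secondary objective, and SAP 5.11.1.1 calls the efficacy part an estimation study. The estimate and its interval are therefore the product of these two analyses, and the rule acts on both. The upper limit works the same way at the other end.

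**Working it through.** **Figures in the plan.** The documents give no LLOQ, share below the limit (BLQ share), SD or effect size for any biomarker, so there is no biomarker figure to reproduce. The group sizes, 28 and 14 evaluable, come from the Protocol synopsis. The related enrolment figure reproduces: 42 / 0.85 = 49.4, rounded up to 50.

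**Assumptions not in the documents.** Log10 values are normal with SD 0.30 in both arms; the correlation of baseline with Month 6 is 0.7; treatment is a pure shift d = log10(true ratio). The BLQ share f is that of baseline (and of placebo at Month 6), varied from 5% to 30%.

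**Step 1: bias in closed form.** With limit c = 0.30 × Φ⁻¹(f) and z = (c − μ)/0.30, the mean after substitution is

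E[max(Y, c)] = μ + (c − μ)Φ(z) + 0.30 φ(z).

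Baseline is balanced by randomisation, so the ANCOVA difference estimates the difference between arms in this quantity. For f = 20% and a true ratio of 0.70:

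- c = 0.30 × (−0.8416) = −0.2525; d = log10(0.70) = −0.1549.
- Placebo: 0 + (−0.2525)(0.20) + 0.30 × 0.2800 = 0.0335.
- Active: z = (−0.2525 + 0.1549)/0.30 = −0.325, so 37% of Month 6 values are BLQ. The mean is −0.1549 + (−0.0976)(0.3725) + 0.30 × 0.3784 = −0.0777.
- Difference: −0.0777 − 0.0335 = −0.1112, a ratio of 0.774 instead of 0.70.

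**Step 2: size against sampling error.** Without censoring, SE = 0.30 × √(1 − 0.49) × √(1/28 + 1/14) = 0.070 log10. The 20% shift is (0.1549 − 0.1112)/0.070 = 0.6 SE. The same formula at 10% gives a difference of −0.1308, a shift of 0.024, or about one third of an SE.

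**Step 3: simulation of the SAP model**, setting baseline and Month 6 values below c to c, with t-based 95% limits:

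| Baseline BLQ share | True ratio 0.70: estimate | Coverage | True ratio 0.80: estimate | Coverage |
|---|---|---|---|---|
| 5% | 0.72 | 94% | 0.81 | 95% |
| 10% | 0.74 | 93% | 0.82 | 94% |
| 20% | 0.78 | 86% | 0.85 | 92% |
| 30% | 0.81 | 73% | 0.87 | 88% |

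At a true ratio of 0.70 the mean CI width in log10 units falls from 0.285 without censoring to 0.263, 0.248, 0.221 and 0.195 down the table.

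**Step 4: no treatment effect.** The estimated ratio is 1.00, coverage about 95%, and rejection at two-sided 0.20 about 19–22%. The interval is still narrower, but it covers correctly.

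**Step 5: censored fit.** A Tobit model with the same terms, Month 6 left-censored at the LLOQ and a BLQ baseline left at the LLOQ, returns 0.70 at a true ratio of 0.70. Coverage is 94–96% with t-based limits; runs with normal-based limits gave 91–94%. Its interval widens as the BLQ share rises: at a true ratio of 0.80, 0.27 log10 at 10%, 0.29 at 25% and 0.31 at 50%.

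**Step 6: sensitivity to the assumptions.** At 25% BLQ with SD from 0.2 to 0.4, coverage under the SAP rule is 83–92% at a true ratio of 0.80 and 15–77% at 0.60.

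**The case against.** The strongest objection is that nothing shows the problem will arise. No document gives a BLQ share, and the only remark on the NfL distribution is about skew and extreme values, not a floor. This stands, and it is why the point is conditional. At 5–10% the estimate moves by about a third of an SE or less at a true ratio of 0.70, and coverage stays at 93–95% over the two ratios shown. The assumed ratios also have no source in the documents.

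The loss of signal is modest too. At a true ratio of 0.80, rejection at two-sided 0.20 falls only from about 53% to 42% even at 50% BLQ. These are secondary endpoints in an exploratory safety trial. The primary endpoint and the sample size are untouched.

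Several stronger readings are tempting, and the documents do not support them:

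- **False-positive findings, or an interval that is wrong in general.** With equal spread and no effect, type I error and coverage are nominal. The fault appears only when the true ratio differs from 1.
- **Bias always towards 1.** This needs similar spread in both arms. If the SD in one arm is 0.7 or 1.3 times the other with no mean shift, substitution alone gives ratios of about 0.92–0.97 or 1.05–1.09 at 10–50% BLQ.
- **A problem no reader could detect.** SAP 5.3 lists all data and reports minimum and first quartile for continuous variables. With 25% or more of values at the limit these two coincide, so heavy piling would show. A count is clearer, but its absence does not hide the harmful case.
- **A flaw in every biomarker comparison.** Only NfL light chain and TDP-43 are compared in a model.

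One practical objection also stands: a standard Tobit model censors the response only, so the plan must say how a BLQ baseline enters.

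**Conclusion.** The point holds conditionally. The rule is explicit and feeds two between-arm estimates with nothing to check it. Under the stated assumptions, the distortion becomes material at about 20% of baseline values BLQ, given a real effect and similar spread. The error in the ratio is then about 0.08 to 0.11 at a true ratio of 0.70 (0.78 − 0.70 and 0.81 − 0.70) and 0.05 to 0.07 at 0.80, with the coverage loss shown above. Below about 10% there is little to gain from a change.

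Whether either assay reaches such shares cannot be learned from the documents. This is therefore an inexpensive improvement to a secondary analysis. It is not evidence that the planned NfL or TDP-43 result will be wrong.

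**What to change.** Before unblinding, amend SAP 5.11.5 as follows:

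1. For all biomarkers, report n (%) BLQ and ALQ by arm and visit.
2. For NfL light chain and TDP-43, add the same log10 model with Month 6 values left-censored at the LLOQ and right-censored at the ULOQ (Tobit, for example PROC LIFEREG) as a prespecified sensitivity analysis.
3. Make that model the main analysis if the blinded pooled BLQ/ALQ share exceeds a prespecified level. State the visit at which the share is counted, because an effect raises it at Month 6. For example, 20% at baseline with a true ratio of 0.70 gives a pooled Month 6 share of about (2 × 37% + 20%)/3 = 31%.
4. State that a BLQ baseline covariate stays at the LLOQ in that model.

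The cost is a few lines of SAP text and code. The downsides are reliance on log-normality, which the planned log10 ANCOVA and geometric-mean ratios already lean on, and a wider interval. If no values are censored, the counts will show it and the estimated ratio is unchanged.

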5.11.5.2.1 Analysis of NFL

NFL missing values will not be imputed.

As NFL distribution might be rather skewed with extreme values, NFL assessed at baseline and at month 6 will be log10 transformed. A descriptive analysis will be performed on the log10-scale and then back-transformed: geometrical means and their 95% Cis will be provided.

NFL (log10 transformed) at month 6 will be analyzed in an ANCOVA model adjusting for treatment and baseline NFL (log10 transformed). Adjusted means and the difference in adjusted means will be estimated in this model and then back transformed into the original scale. Adjusted mean NFL at month 6 in each treatment is interpreted as a geometric mean (adjusted for baseline

STATISTICAL ANALYSIS PLAN		
InFlectis BioScience	Sponsor:	InFlectis BioScience
	Protocol Number:	P288ALS
VERSION 1.0 NOV 12, 2024		

NFL). The back transformed adjusted treatment difference is interpreted as the ratio of adjusted geometric means between treatments.

A descriptive analysis will only be performed on the log10-scale and then back-transformed: geometrical means and their 95% CIs will be also provided at 3 months.

5.11.5.2.2 Analysis of TDP-43

TDP-43 will be analyzed with the same approach as for NFL on the FAS.

5.11.5.2.3 Other biomarkers.

A descriptive analysis will only be performed on the log10-scale and then back-transformed: geometrical means and their 95% Cis will be provided on the FAS.

5.11.6 Change in Bioelectrical impedance

5.11.6.1.1 Parameters

Bioelectrical parameters are:

- Phase angle,
- Z200/Z5 impedance ratio,
- Skeletal muscle mass,
- Dry mass
- Dry mass without fat
- Mineral bone content
- ECM/BCM ratio ECM
- Energy expenditure

5.11.6.1.2 Expressions

These parameters will be expressed in terms of:

- Value at baseline and at each planned visit (baseline (V0), V3, and V4).
- Change from baseline to each post baseline visit.

5.11.6.1.3 Analysis

A descriptive analysis will be provided only at each visit by treatment group on FAS.

5.11.7 Change in ALSAQ-40 at Month 6 (V4)

STATISTICAL ANALYSIS PLAN		
InFlectis BioScience	Sponsor:	InFlectis BioScience
	Protocol Number:	P288ALS
VERSION 1.0 NOV 12, 2024		

5.11.7.1.1 Expressions

These parameters will be expressed in terms of:

- Value at baseline and at V4.
- Change from baseline to V4.

5.11.7.1.2 Analysis

A descriptive analysis will be provided only on the FAS.

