QoL will be assessed using the validated ALSAQ-40 questionnaire, specifically used to measure the subjective well-being of patients with ALS [\[43\]](#). ALSAQ-40 has psychometric robustness, and it provides an interpretable picture of the impact of the condition on the subjective functioning and well-being of patients on areas that are of concern to them. It provides scores for 5 areas of health state: physical mobility (10 items), activities of daily living and independence (10 items), eating and drinking (3 items), communication (10 items), and emotional reactions (10 items). The questionnaire must be completed by the patient. Patients need to tick the box which best describes his/her own experience or feelings. Patients should try to answer every question even though some may seem rather similar to others, or may not seem relevant to them. QoL will be assessed as the change in absolute value and percentage of ALSAQ- 40 between baseline and 6 months.

4.2.2.5 *Biobank*

Blood, urine and CSF samples will be stored at -80°C at a facility designated by the sponsor to measure biomarker candidates as needed. These samples will be kept for 5 years after final database lock for further analysis and then destroyed if unused.

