Changes in plasma concentration of inflammatory and oxidative stress biomarkers will be measured from baseline to 3 months, and from baseline to 6 months. All changes will be compared between both arms.

Correlation of biomarkers with clinical endpoints will be assessed.

QoL endpoint

Change in ALS-AQ40 QoL scores from baseline will be assessed at 6 months and compared between both arms.

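### The protocol promises between-arm comparisons of ALSAQ-40 and all biomarkers; the SAP keeps them only for NfL light chain and TDP-43 and does not declare the reduction

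*SAP*

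**What the plan says.** **Protocol.** Section 8.1.5.2 says of quality of life: "Change in ALS-AQ40 QoL scores from baseline will be assessed at 6 months and compared between both arms". On biomarkers it says: "All changes will be compared between both arms". The synopsis repeats both. In the section 2 table the biomarker endpoints are worded as comparisons with placebo; the ALSAQ-40 endpoint is worded only as change to 6 months.

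**SAP, ALSAQ-40.** Section 5.11.7 expresses ALSAQ-40 as the value at baseline and V4 and the change between them. The whole analysis is: "A descriptive analysis will be provided only on the FAS".

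**SAP, biomarkers.** Section 5.11.5.2.1 does give a treatment comparison for neurofilament: "NFL (log10 transformed) at month 6 will be analyzed in an ANCOVA model adjusting for treatment and baseline NFL (log10 transformed)". It adds: "The back transformed adjusted treatment difference is interpreted as the ratio of adjusted geometric means between treatments". Section 5.11.5.2.2 applies the same approach to TDP-43. For all other markers section 5.11.5.2.3 says: "A descriptive analysis will only be performed on the log10-scale and then back-transformed", giving geometric means and their 95% CIs.

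**SAP section 7** declares two changes to the protocol's analysis: ANCOVA in place of the MMRM, with new handling of deaths, and removal of the Bayesian analysis. It mentions neither ALSAQ-40 nor the biomarkers.

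**The concern.** Quality of life and biomarkers are secondary objectives in both documents. The protocol says the arms will be compared on them, and for ALSAQ-40 and most markers the SAP contains no step that does so. A reader of the eventual report who checks it against the protocol would find promised comparisons missing with no explanation. Any comparison added later would be post hoc: SAP section 5 sends analyses added after database lock to an addendum.

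The loss is one of interpretation. The protocol calls this mainly an estimation trial, so the useful product is an estimate with its uncertainty. Separate summaries for 28 and 14 patients invite the eye to subtract one column from the other without an interval, and without adjustment for baseline differences that unstratified randomisation at this size can leave.

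**Working it through.** **Step 1. Set the commitments beside the plan.**

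| Outcome | Protocol | SAP | In section 7? |
|---|---|---|---|
| NfL light chain | arms compared | ANCOVA, adjusted ratio | kept |
| TDP-43 | arms compared | same ANCOVA | kept |
| NfL heavy chain | arms compared | apparently descriptive | no |
| Inflammatory and oxidative stress markers | arms compared, months 3 and 6 | descriptive | no |
| ALSAQ-40 | arms compared, month 6 | descriptive | no |

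Heavy chain is an inference. The SAP's abbreviation list and its subgroup definition (5.2.23) expand NFL as light chain, so the ANCOVA section reads as light chain only. Section 5.11.5.1 also uses NfL as a prefix for heavy chain, so the text is not beyond doubt.

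**Step 2. Count the affected markers.** SAP 5.11.5.1 lists 22. Removing NfL light chain and TDP-43 leaves 22 − 2 = 20.

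- Traceable to protocol 4.2.2.3: heavy chain (1), the ten named inflammatory markers from IL-6 to VEGF (10), and TGFβ, which the SAP splits into three (3), giving 14.
- 8-hydroxy 2 deoxyguanosine makes 15 if it stands for the protocol's oxidative stress class, which is my assumption.
- The other 5 (growth differentiation factor 15, fibroblast growth factor 21, NGFR/p75ECD, neopterin and creatinine) are not named in that section.

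**Step 3. Precision of a restored comparison.** Inputs: 28 and 14 evaluable patients (protocol synopsis). Neither document gives an ALSAQ-40 or marker SD, so the unit is the SD of the analysed outcome, with a normal approximation.

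- SE = √(1/28 + 1/14) = 0.327 SD
- 80% half-width = 1.282 × 0.327 = 0.42 SD
- 95% half-width = 1.960 × 0.327 = 0.64 SD
- Power at one-sided 0.10 is 36%, 60% and 88% for assumed effects of 0.3, 0.5 and 0.8 SD. These effects are illustrative.

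**Step 4. Price of restoring it.** Five ALSAQ-40 domains plus 15 markers make 20 further month-6 comparisons. At the SAP's two-sided 0.20 with no multiplicity adjustment, 20 × 0.20 = 4 would be expected to be nominally positive if nothing differed. Taking all 20 markers gives 25 × 0.20 = 5.

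**Step 5. ALSAQ-40 item counts.** Protocol 4.2.2.4 gives 10 items for mobility, 10 for daily living, 3 for eating and drinking, then "communication (10 items), and emotional reactions (10 items)". The sum is 10 + 10 + 3 + 10 + 10 = 43 for a 40-item form. In appendix 17.1.4, grouped by content, communication is items 24 to 30, which is 7, and 10 + 10 + 3 + 7 + 10 = 40. The SAP gives no ALSAQ-40 scoring rule: no domain score, total or missing-item rule.

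**The case against.** The strongest defence is that this is an exploratory safety study with no formal sample size calculation. The quality-of-life objective is only to investigate, the ALSAQ-40 endpoint does not mention placebo, and the protocol names no test or model for it. SAP 5.3 presents summaries by treatment group or overall, so a by-arm display is possible, and the other markers do get geometric means with intervals. Adding some 20 unadjusted comparisons brings noise. Values below the limit of quantification are set to that limit (SAP 5.11.5.2), which may make an ANCOVA unsuitable for some markers.

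Much of this stands, and it keeps the point minor. It also means that restoring every listed marker is not clearly warranted. It does not remove the mismatch. The analysis section of the protocol does promise the comparison, a by-arm summary is not a between-arm estimate, and section 7 is silent. SAP 5.11.7.1.2 does not even say that the ALSAQ-40 summary is by arm, whereas the bioimpedance section does.

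Three stronger readings are tempting and are not supported:

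- **That the SAP compares the arms on no biomarker.** It does so for NfL light chain and TDP-43.
- **That the quality-of-life objective goes unanswered.** ALSAQ-40 is still described at baseline and month 6. What is missing is a comparative estimate.
- **That ALSAQ-40 will be mis-scored.** If a program divided by 10 communication items, with items coded 0 to 4 and rescaled to 100, the maximum would be 28/40 = 70. Neither document states that coding, that scaling or any formula using the count of 10.

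**Conclusion.** The point holds in limited form. The between-arm comparisons that the protocol promises for ALSAQ-40 and for biomarkers other than NfL light chain and TDP-43 are reduced to description, and the SAP does not declare it. Up to 20 of 22 markers are affected; 14 or 15 of them trace to the protocol's own list. That NfL heavy chain is among them rests on reading NFL as light chain.

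No bias in a planned result is shown. The cost is the absence of a pre-specified estimate, whose 95% interval would be about ±0.64 SD if 28 and 14 patients are evaluable. The sum of 43 is a clerical slip with no demonstrated effect on results.

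**What to change.** Before unblinding:

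1. Apply the NfL ANCOVA structure (treatment and baseline value) to the month-6 ALSAQ-40 domain scores: items 1–10, 11–20, 21–23, 24–30 and 31–40. State how each score is formed and how missing items are treated.
2. Apply it on the log10 scale to NfL heavy chain and to the protocol-named inflammatory and oxidative stress markers. For the latter two groups, either compare the arms at month 3 as well or declare that month 3 stays descriptive.
3. Report the adjusted difference, or ratio of geometric means, with 80% and 95% CIs, labelled exploratory with no multiplicity claim.
4. Keep a marker descriptive where many values lie at a quantification limit. List in section 7 every promised comparison that stays descriptive.
5. Correct the communication count in protocol 4.2.2.4 to 7.

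The cost is a few SAP lines, reuse of an existing model, and about 20 more unadjusted exploratory estimates, some of which will look positive by chance. The NfL analysis imputes nothing, so reusing it describes patients alive and assessed at month 6; the SAP should say so. If the sponsor prefers no added comparisons, declaring the reduction in section 7 makes the plan transparent but does not recover the promised estimates.
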